5.4.1.2.2. Sensitivity Estimators of the Main Estimand for the KSE1

Sensitivity analyses will be conducted by constructing a sensitivity estimator for the main estimand of KSE1 as defined in Section 5.4.1.2. This sensitivity estimator will be similar to the one defined for the main estimand of the primary endpoint, i.e it will use Missing as Non-Response data imputation rule.

5.4.1.2.2.1. Sensitivity Estimator of the Main Estimand (Missing as Non-Response) for the KSE1

For this sensitivity estimator, the same statistical model (stratum-adjusted MH test) and data included will be used as for the main estimator (Section 5.4.1.2.1). The assumption for missing data and the rule to handle missing data have changed.

5.4.1.2.2.1.1. Assumptions

- Missing Data for HDV RNA are Missing Not At Random (MNAR)
- The treatment effect is homogeneous across strata

5.4.1.2.2.1.2. Missing Data Handling Rule

Participants who withdraw from the study prior to Week 48 will be considered as non-responders. All participants with missing HDV RNA data for the determination of the KSE1 will be imputed as non-responders.

5.4.1.2.3. Supplementary Estimators of the Main Estimand for the KSE1

Supplementary analyses to better interpret the results will be conducted by constructing additional estimator for the main estimand of the KSE1 as defined in Section 5.4.1.2. This supplementary estimators will be similar to the sensitivity estimator of the main estimand (Section 5.4.1.2.2) but based on the mITT set (instead of ITT) for participants in Part 2: mITT + Missing as Non-Response (Supplementary Estimator). The supplementary estimator analysis will only be performed if there is a difference of more than 5% from ITT to mITT.

5.4.2. KSE2: Normal ALT at Week 48

5.4.2.1. Definition

The second key secondary efficacy endpoint is defined as the proportion of participants with normal ALT at Week 48.

5.4.2.2. Main Estimand for the KSE2

Study Objective: To evaluate the efficacy of JNJ-3989 + NA regimen versus Placebo + NA in reducing liver inflammation.

Scientific question: in the adult population co-infected with HBV and HDV, what is the benefit of JNJ-3989 (100mg Q4W) in combination with NA for 48 weeks in reducing liver inflammation?

The main analysis of this endpoint will be addressed by using the following estimand attributes:

A) Study Intervention:

- Arm 1: JNJ-3989+NA
- Arm 2: NA alone

B) Study population: Non-cirrhotic patients 18 to 65 years of age, inclusive, with HBV/HDV co-infection.

C) Variable: Response status defined as having normal ALT at Week 48

D) Intercurrent events:

- Treatment discontinuation prior to Week 48 if the participant discontinued treatment prior to Week 48 then the participant will be considered as non-responder (composite strategy).
- Selected major protocol deviations affecting efficacy: 0 identifies deviations considered as ICEs. Participants with such deviations and who have missing data for ALT at Week 48 will be considered as non-responders (composite strategy).
- Deaths prior to Week 48 are handled in a composite strategy as participants who die prior to Week 48 will be considered as non-responders.

E) Population level summary: Difference in proportion of responders defined by KSE2 between the two intervention arms.

5.4.2.2.1. Main Estimator of the Main Estimand for the KSE2

5.4.2.2.1.1. Analysis Methods

Statistical Model

The same stratum-adjusted MH test on the difference of proportions as described for the main estimator of the main estimand for the primary endpoint will be used (see Section 5.3.2.1).

5.4.2.2.1.2. Data Included

All available data from ITT analysis set in Part 2, after taking into account all the ICEs and applying the ICE strategies specified in the previous Section 5.4.2.2, will be included.

5.4.2.2.1.3. Assumptions

- Missing Data for ALT are Missing At Random (MAR)
- The treatment effect is homogeneous across strata

5.4.2.2.1.4. Missing Data Handling Rule

- Participants who withdraw from the study prior to Week 48 will be considered as non-responders.
- For participants who remain in the study at Week 48 after experiencing a major protocol deviation defined for the purpose of efficacy analyses, which is an ICE, and have missing ALT at Week 48, then the imputation to non-response will be applied. If the ALT value for the KSE2 at Week 48 is available, then such data will be used to determine their response status.

- For participants who remain the study at Week 48, have had no major protocol deviations defined as ICE and have the values of ALT available, such data will be used to determine their response status.
- For the participants who remain in the study at Week 48 and who have not experienced any major protocol deviations defined for the purpose of efficacy analyses as ICE, and has missing ALT values missing at Week 48, then missing data will be imputed by the values obtained from the MI model performed for the main estimator of the primary efficacy endpoint to leverage the correlations between HDV RNA and ALT values (see Section 5.3.2.1.4). Once the ALT values at Week 48 are obtained, the binary key secondary endpoint will be derived and analyzed as described in Section 5.3.2.1.

5.4.2.2.2. Sensitivity Estimators of the Main Estimand for the KSE2

Sensitivity analyses will be conducted by constructing a sensitivity estimator for the main estimand of KSE2 as defined in Section 5.4.2.2. This sensitivity estimator will be similar to the one defined for the main estimand of the primary endpoint, i.e it will use different Missing as Non-Response data imputation .

5.4.2.2.2.1. Sensitivity Estimator of the Main Estimand (Missing as Non-Response) for the KSE2

For this sensitivity estimator, the same statistical model (stratum-adjusted MH test) and data included will be used as for the main estimator (Section 5.4.2.2.1). The assumption for missing data and the rule to handle missing data have changed.

5.4.2.2.2.1.1. Assumptions

- Missing Data for ALT are Missing Not At Random (MNAR)
- The treatment effect is homogeneous across strata

5.4.2.2.2.1.2. Missing Data Handling Rule

Participants who withdraw from the study prior to Week48 will be considered as non-responders. All participants with missing ALT data for the determination of the KSE2 will be imputed as non-responders.

5.4.2.2.3. Supplementary Estimators of the Main Estimand for the KSE2

Supplementary analysis to better interpret the results will be conducted by constructing additional estimator for the main estimand of the KSE2 as defined in Section 5.4.2.2. This supplementary estimator will be similar to the sensitivity estimator of the main estimand (5.4.2.2.2) but based on the mITT set (instead of ITT) for participants in Part 2 : mITT + Missing as Non-Response (Supplementary Estimator). The supplementary estimator analysis will only be performed if there is a difference of more than 5% from ITT to mITT.

5.4.2.2.4. Main Estimator of the Supplementary Estimand for the KSE2

5.4.2.2.4.1. Analysis Methods

Statistical Model

Similar stratum-adjusted MH test on the difference of proportions as described for the main estimator of the main estimand will be used (see section 5.4.1.2.1).

5.4.2.2.4.2. Data Included

All available data from randomized participants in Part 2 that are included in the mITT analysis set will be used, after taking into account the ICEs and applying the ICE strategies specified in Section 5.4.2.2.

5.4.2.2.4.3. Assumptions

- The treatment effect is homogeneous across strata

5.4.2.2.4.4. Missing Data Handling Rule

Participants who withdraw from the study prior to Week 48 will be considered non-responders. For the participants who remain in the study at Week 48 and who have not experienced an ICE as listed in 0, but with ALT values missing at Week 48, then the method to handle missing data will be the imputation to non-responder.

5.4.3. KSE3: HBsAg Seroclearance at Week 48

5.4.3.1. Definition

The third key secondary efficacy endpoint is defined as the proportion of participants with HBsAg seroclearance i.e. with HBsAg (quantitative) < LLOQ (see Table 4) at Week 48.

5.4.3.2. Main Estimand for the KSE3

Study Objective: To evaluate the efficacy of JNJ-3989 + NA regimen versus Placebo + NA in reducing HBsAg levels.

Scientific question: in the adult population co-infected with HBV and HDV, what is the benefit of JNJ-3989 (100mg Q4W) in combination with NA compared with Placebo + NA for 48 weeks in reducing HBsAg levels?

The main analysis of this endpoint will be addressed by using the following estimand attributes:

A) Study Intervention:

- Arm 1: JNJ-3989+NA
- Arm 2: NA alone

B) Study population: Non-cirrhotic patients 18 to 65 years of age, inclusive, with HBV/HDV co-infection.

C) **Variable:** HBsAg level at Week 48

D) **Intercurrent events:**

- Treatment discontinuation prior to Week 48: if the participant discontinued treatment prior to Week 48 then the participant will be considered as non-responder (composite strategy).
- Selected major protocol deviations affecting efficacy: 0 identifies deviations considered as ICEs. Participants with such deviations and who have missing data for HBsAg at Week 48 will be considered as non-responders (composite strategy).
- Deaths prior to Week 48 are handled in a composite strategy as participants who die prior to Week 48 will be considered as non-responders.

E) **Population level summary:** Difference in proportion of participants with HBsAg seroclearance at Week 48 between the two intervention arms.

5.4.3.2.1. Main Estimator of the Main Estimand for the KSE3

5.4.3.2.1.1. Analysis Methods

Statistical Model

The same stratum-adjusted MH test on the difference of proportions as described for the main estimator of the main estimand for the primary endpoint will be used (see Section 5.3.2.1).

5.4.3.2.1.2. Data Included

All available data from ITT analysis set in Part 2, after taking into account all the ICEs and applying the ICE strategies specified in the previous Section 5.4.3.2, will be included.

5.4.3.2.1.3. Assumptions

- Missing Data for HBsAg are Missing At Random (MAR)
- The treatment effect is homogeneous across strata.

5.4.3.2.1.4. Missing Data Handling Rule

- Participants who withdraw from the study prior to Week 48 will be considered as non-responders.
- For participants who remain in the study at Week 48 after experiencing a major protocol deviation defined for the purpose of efficacy analyses, which is an ICE, and have missing HBsAg at Week 48, then the imputation to non-response will be applied. If the HBsAg value for the KSE4 at Week 48 is available, then such data will be used to determine their response status.
- For participants who remain the study at Week 48, have had no major protocol deviations defined as ICE and have the values of HBsAg available, such data will be used to determine their response status.

- For the participants who remain in the study at Week 48 and who have not experienced any major protocol deviations defined for the purpose of efficacy analyses as ICE, and have missing HBsAg values missing at Week 48, missing data will be imputed using a MI model.

The MI model will use all available data and be applied to the continuous HBsAg values (not the binary endpoint). Of note, also the pre-ICE data for those subjects who experienced an ICE will be included in the MI model; but for these subjects the response status will be applied according to the ICE strategies before running the MI model.

The MI model will include treatment, the 3 randomization factors, the available non-missing log-transformed HBsAg (values < LLOQ will be first substituted following rules described in [Table 4](#)) for each scheduled time point (Week) and the following demographic and baseline characteristics^{4,6}: age, gender, and baseline value for HDV RNA level, ALT level, HBsAg level, and HBV DNA level.

The details on the implementation of this MI model will follow the same steps as described in Section [5.3.2.1.4](#).

5.4.4. KSE4 : Reduction in LSM From baseline to Week 48

5.4.4.1. Definition

The fourth key secondary efficacy endpoint is defined as the proportion of participants with LSM reduction ≥ 2 kPa from baseline to Week 48 as assessed by vibration-controlled transient elastography (VCTE) (FibroScan).

5.4.4.2. Main Estimand for the KSE4

Study Objective: To evaluate the efficacy of JNJ-3989 + NA regimen versus Placebo + NA in reducing liver fibrosis.

Scientific question: in the adult population co-infected with HBV and HDV, what is the benefit of JNJ-3989 (100mg Q4W) in combination with NA compared with Placebo + NA for 48 weeks in reducing liver fibrosis determined using LSM?

The main analysis of this endpoint will be addressed by using the following estimand attributes:

A) Study Intervention:

- Arm 1: JNJ-3989+NA
- Arm 2: NA alone

B) Study population: Non-cirrhotic patients 18 to 65 years of age, inclusive, with HBV/HDV co-infection

C) Variable: Response status defined as having reduction in LSM from baseline ≥ 2 kPa at Week 48 as assessed by VCTE (Fibroscan)

D) Intercurrent events:

- Treatment discontinuation prior to Week 48: if the participant discontinued treatment prior to Week 48 then the participant will be considered as non-responder (composite strategy).
- Selected major protocol deviations affecting efficacy: 0 identifies deviations considered as ICEs. Participants with such deviations and who have missing data for LSM at Week 48 will be considered as non-responders (composite strategy).
- Deaths prior to Week 48 are handled in a composite strategy as participants who die prior to Week 48 will be considered as non-responders.

E) Population level summary: Difference in proportion of responders defined by KSE3 between the two intervention arms.

5.4.4.2.1. Main Estimator of the Main Estimand for the KSE4**5.4.4.2.1.1. Analysis Methods****Statistical Model**

The same stratum-adjusted MH test on the difference of proportions as described for the main estimator of the main estimand for the primary endpoint will be used (see Section 5.3.2.1).

5.4.4.2.1.2. Data Included

All available data from ITT analysis set in Part 2, after taking into account all the ICEs and applying the ICE strategies specified in the previous Section 5.4.4.2, will be included.

5.4.4.2.1.3. Assumptions

- Missing Data for LSM are Missing At Random (MAR)¹²
- The treatment effect is homogeneous across strata.

5.4.4.2.1.4. Missing Data Handling Rule

- Participants who withdraw from the study prior to Week 48 will be considered as non-responders.
- For participants who remain in the study at Week 48 after experiencing a major protocol deviation defined for the purpose of efficacy analyses, which is an ICE, and have missing LSM at Week 48, then the imputation to non-response will be applied. If the LSM value for the KSE3 at Week 48 is available, then such data will be used to determine their response status.
- For participants who remain the study at Week 48 and have had no major protocol deviations defined as ICE and have the values of LSM available, such data will be used to determine their response status.
- For the participants who remain in the study at Week 48 and who have not experienced any major protocol deviations defined for the purpose of efficacy analyses as ICE, and has missing LSM values at Week 48, then they will be considered as non-responder (composite strategy).

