2.3. Analysis Sets

Due to the issues caused by the pandemic Coronavirus Disease (COVID-19), the study team had decided to add the Modified Intent-to-treat analysis set (mITT) as defined below. It will be used for the efficacy analyses instead of the ITT in case of significant impact of future pandemics on the conduct and data collection for this study. The assessment of the impact will be made before the primary analysis of Part 2, however, the mITT is tentatively planned to be used if 6 or more participants are affected.

All randomized analysis set: All participants who were randomly assigned to an intervention arm in the study. Participants will be analyzed according to the study intervention they were randomly assigned to.

Intent-to-Treat analysis set (ITT): All participants who were randomly assigned to an intervention arm and who received at least 1 dose of study intervention. Participants will be analyzed according to the study intervention they were randomly assigned to.

Modified Intent-to-Treat analysis set (mITT): All participants who were randomized in the study and received at least one dose of study treatment excluding those participants impacted by the pandemic defined as those participants who, because of COVID-19 or similar pandemics related reasons, withdrew prematurely from the study prior to Week 48, or had no efficacy assessment for the primary endpoint. COVID-19 or similar pandemics related reasons may include for example missed visits due to travel restriction, shortage of lab kits at the planned visit, missed collection of blood sample at key time points for the primary efficacy endpoint, etc. Participants will be analyzed according to the study intervention they were randomly assigned to.

Safety analysis set: All participants who take at least 1 dose of study intervention. Participants will be analyzed according to the study intervention they actually received.

Pharmacokinetics analysis set (PK): The PK analysis set is defined as subjects who have received at least 1 dose of any of the study treatments and have at least 1 valid blood sample drawn for PK analysis.

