5.5.1.1.13. Liver Stiffness Measurement

The proportion of participants with the following LSM changes from baseline (both in terms of reductions and increases) will be evaluated over time:

- ≥ 1 kPa
- ≥ 2 kPa
- ≥ 4 kPa
- ≥ 6 kPa

Only participants from sites with available VCTE (Fibroscan) will be included in the analysis. Within these participants, missing LSM (in kPa) at a specific timepoint will be considered as non-responders for that timepoint.

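### KSE4 keeps participants from sites without VCTE as LSM non-responders while SAP 5.5.1.1.13 leaves them out, and the latter section also counts a missing scan as no worsening

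*SAP*

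**What the plan says.** **KSE4 (SAP 5.4.4).** The endpoint is the proportion with an LSM reduction of at least 2 kPa from baseline to Week 48 by FibroScan. The data included are "All available data from ITT analysis set in Part 2". SAP 2.3 defines ITT as "All participants who were randomly assigned to an intervention arm and who received at least 1 dose of study intervention", with no condition on equipment.

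The missing-data rule in 5.4.4.2.1.4 leads to non-response by every route:
- Participants who withdraw before Week 48 are non-responders.
- Those with an intercurrent deviation "and have missing LSM at Week 48, then the imputation to non-response will be applied".
- A participant still in the study without such a deviation who "has missing LSM values at Week 48, then they will be considered as non-responder (composite strategy") is also a failure.

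The assumption printed above these rules is "Missing Data for LSM are Missing At Random (MAR").

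**Other secondary LSM analysis (SAP 5.5.1.1.13).** Changes of at least 1, 2, 4 and 6 kPa are evaluated over time, as reductions and as increases. Here "Only participants from sites with available VCTE (Fibroscan) will be included in the analysis", and within that group "missing LSM (in kPa) at a specific timepoint will be considered as non-responders for that timepoint". The parent section, 5.5, says that other secondary endpoints use observed cases without imputation.

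**The concern.** The 2 kPa reduction at Week 48 appears in both sections, with two different populations. A participant at a site without VCTE cannot have an LSM, yet is a failure in KSE4 and is absent from 5.5.1.1.13. The KSE4 rate would then partly reflect where participants enrolled. For HBsAg, SAP 5.5.1.1.7 explains why the key secondary and over-time analyses treat Week 48 differently; for LSM there is no explanation of the differing site restriction. The primary endpoint, KSE1 and KSE2 each have a sensitivity estimator. KSE4 has none that would show the effect of the denominator.

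The second matter lies only in 5.5.1.1.13. Counting missing as non-response is conservative for a benefit. For an LSM increase it works the other way, because a missing scan becomes no increase. In a trial where ALT elevations led to a halt in enrolment, the reported frequency of liver stiffness worsening should not depend on that default.

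**Working it through.** The SAP gives no LSM response rate, no worsening rate and no count of participants at sites without VCTE, so there is no LSM figure of its own to reproduce. The documents supply the rules, the Part 2 size of 30 (SAP 1.2) and the 4:1 allocation, which implies about 24 in Arm 1 and 6 in Arm 2. All rates below are assumptions.

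**1. Tracing one participant.** Take a Part 2 participant who is dosed, remains in the study, has no intercurrent deviation and attends a site without VCTE.
- KSE4: in ITT, Week 48 LSM missing, so non-responder.
- SAP 5.5.1.1.13: excluded.
- Attachment 1, item 21, lists LSM not done at Week 48 as not an intercurrent event, so the third KSE4 route applies. That route is labelled a composite strategy although no listed intercurrent event has occurred.

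**2. Dilution of KSE4, equal shares.** If a share f of each arm has no device and the true rates are p1 and p2, the expected KSE4 difference is (1 − f)(p1 − p2). With assumed rates of 40% and 10%, the true difference is 30 points.

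| f | KSE4 difference |
|---|---|
| 0% | 30 points |
| 10% | 0.90 × 30 = 27 points |
| 20% | 0.80 × 30 = 24 points |
| 30% | 0.70 × 30 = 21 points |

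**3. Unequal shares at 24:6.** One participant is 1/24 = 4.2 points of the Arm 1 denominator and 1/6 = 16.7 points of the Arm 2 denominator. With k1 and k2 participants at sites without VCTE, the expected difference is p1(24 − k1)/24 − p2(6 − k2)/6. With no true effect and both rates at an assumed one third:
- k1 = 0, k2 = 2: 33.3% − 22.2% = +11.1 points for Arm 1.
- k1 = 6, k2 = 0: 25.0% − 33.3% = −8.3 points.

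The sign therefore depends on which arm has more such participants.

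**4. Worsening in 5.5.1.1.13.** If a share m of scans is missing, unrelated to worsening, a true rate w is reported as w(1 − m).
- w = 10%, m = 20%: 0.10 × 0.80 = 8%.
- w = 20%, m = 10%, 20%, 30%: 18%, 16%, 14%.

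As the other bound, suppose 20% of scanned participants worsen and everyone with a missing scan has worsened too. The true rate is then 0.20(1 − m) + m = 28%, 36% or 44% for the same three values of m.

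**5. The MAR label.** The SAP calls the same missing-as-non-response rule MNAR for the primary endpoint (5.3.2.2.1.1), KSE1 (5.4.1.2.2.1.1) and KSE2 (5.4.2.2.2.1.1). KSE4 applies that rule under a MAR heading.

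**The case against.** A reader might infer that KSE4 is in fact diluted. The documents do not show that. The restriction in 5.5.1.1.13 implies that a site may lack VCTE, but nothing places any of the 30 Part 2 participants at such a site. Whether the device was required there is a protocol matter that is not visible here. The effect could be zero.

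A reader might also infer that understated worsening favours JNJ-3989. The rule applies to both arms, and the comparison is tilted only if missingness, or worsening among those missing, differs between them. The SAP does not say so. Table 1 moves participants who stop treatment into follow-up unless they withdrew consent, and nothing says their scans are lost.

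Nor is measured worsening concealed. LSM values and changes are summarised over time (5.5.1.2, 5.5.2.2), and 5.5.2.2.4 adds a Week 48 ANCOVA and a waterfall plot of individual changes.

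Further, missing as failure in full ITT is a recognised conservative choice. The MAR label changes no number, because KSE4 has no multiple-imputation step. The SAP also never defines non-responder for an increase, so no increase is a reading of loose wording, though the natural one.

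All of this limits the size and direction of the problem. It does not remove the two populations, the conflict with the observed-case rule in 5.5, or the understatement in the reported worsening proportions.

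**Conclusion.** The point holds as a conflict between analysis rules whose numerical effect cannot be determined from the SAP. Followed as written, KSE4 counts any participant who could not be scanned as a failure, 5.5.1.1.13 leaves participants at sites without VCTE out, and a missing scan in 5.5.1.1.13 is taken as no worsening.

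The dilution factor is (1 − f) if the share at sites without VCTE is equal across arms, with f unknown and possibly zero. With about six controls, an imbalance of one or two participants could move the difference either way. The worsening proportion is too low in each arm whenever someone with a missing scan had worsened; the direction of any between-arm bias is unknown. The MAR statement is a labelling error only.

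The study is now descriptive, so estimates and their interpretation are affected and no confirmatory test is. The change is still worth making, because KSE4 is a key secondary endpoint and the reported rates depend on it.

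**What to change.** 1. Use one LSM population in 5.4.4 and 5.5.1.1.13: Part 2 ITT participants at sites with available VCTE (for the Part 2 results in the latter). Define it by site, not by having a baseline scan. Someone at a VCTE site without a baseline LSM would otherwise leave one table and stay in the other.
2. Within that population, keep missing Week 48 LSM as non-response for reductions.
3. Keep full Part 2 ITT with missing as non-response as a KSE4 sensitivity analysis, and state how many participants per arm are at sites without VCTE.
4. Replace MAR with MNAR in the KSE4 assumptions, as the SAP does elsewhere for the same rule.
5. In 5.5.1.1.13, limit missing as non-response to reductions. Report LSM increases on observed cases, with the number missing by arm, and note the exception to 5.5 for reductions.

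The cost is a few lines of SAP text and one extra table, with no new data. The downside is a possibly smaller KSE4 denominator in an already small part of the study. If no Part 2 site lacks VCTE, the two KSE4 analyses coincide.
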